2.3.2 KNOWN POTENTIAL BENEFITS

Participants will receive 10 healthy meals per week during the 8-week study at no cost to them. Participants in the study may feel less stress by saving time on planning, shopping, and preparing meals, improving food insecurity, and may feel good about themselves by eating a healthier diet postpartum. Having a healthier diet and less stress postpartum could have mental and physical health benefits postpartum.

Meal delivery may reduce postpartum weight retention and improve cardiometabolic health management, diet quality, food security, stress, and reduce barriers to healthy eating postpartum. This is important given that approximately 60-75% of women fail to return to their pre-pregnancy weight (i.e., postpartum weight retention) and many women gain weight postpartum. Postpartum weight retention and interpregnancy weight gain are important predictors of long-term obesity risk. Postpartum weight retention and interpregnancy weight gain negatively impact maternal cardiometabolic health and increase risk for adverse outcomes in subsequent pregnancies which are more common among Black women and those of lower socioeconomic status. Black and lower income women are also disproportionately burdened by obesity, which further increases the risk for postpartum weight retention, interpregnancy weight gain, and adverse health outcomes. To-date, traditional diet and weight management programs for postpartum women have been largely unsuccessful. Thus, promotion of healthy diet and postpartum weight loss may improve these outcomes. Participation in this study may enhance our understanding of meal delivery as a strategy for improving maternal health among underserved populations. Given the health risks associated with postpartum weight retention and interpregnancy weight gain, and the challenges of successful weight management postpartum, such information is clinically relevant and has potential for public health impact. Ultimately, results could inform public policy to leverage programs and/or modify insurance coverage to promote sustainability, which would have a meaningful public health impact on both short and long-term maternal health.

3 STUDY DESIGN

3.1 OVERALL DESIGN

This is a single-group intervention trial in which mothers who are 5-45 weeks postpartum and enroll in the trial will receive 10 meals per week for a total of 8-weeks.

Potentially eligible participants will be primarily recruited through the UAB Center for Women's Reproductive Health (CWRH). CWRH nursing staff will prescreen medical records of participants who delivered at UAB. Potentially eligible women will be approached in the postpartum recovery unit following delivery or at their 6-week postpartum appointment by a CWRH research nurse and told about the study. Interested women who meet initial eligibility criteria will be contacted by study staff at 5-45 weeks postpartum to complete a secondary pre-screening via telephone to confirm eligibility. Supplemental recruitment will occur via flyers/ads distributed at UAB obstetrics/gynecological offices, UAB pediatrics clinics, UAB lactation centers, UAB Nurse Family Partnership, local day care centers and churches, local breastfeeding and/or parent support groups, and Birmingham neighborhood associations. Interested women will respond via phone call or email to the public advertisements and be screened by phone.

Interested and eligible women will be scheduled to attend an Enrollment/Baseline Assessment visit during which informed consent will be completed. Those who consent to enroll in the study will then complete baseline study measurements including surveys and anthropometrics.

Within 1-2 weeks of completing the baseline assessment, participants will receive their first study meal delivery order. All participants will receive the study meal delivery intervention for a total of 8-weeks. During the study intervention, participants will be emailed a weekly Qualtrics survey to complete to report intervention adherence.

During the final week of the study meal delivery intervention, participants will complete Follow-up (week 8) assessment visit measurements, including surveys and anthropometrics.

3.2 END OF STUDY DEFINITION

While Primary Completion will be defined as the date of the week 8 follow-up assessment data collection of the last participant, the End of Study will be the date of completion of the participant medical record data abstraction, as these data will provide necessary data to characterize postpartum weight retention and necessary covariates for the conduct of our statistical analyses (e.g., accounting for gestational weight gain).

4 STUDY POPULATION

4.1 INCLUSION CRITERIA

To be eligible women must meet the following inclusion criteria:

- Medicaid eligible and/or have a household income at or below 185 percent of the federal poverty line
- 18 years of age or older

- Initiated prenatal care at a University of Alabama at Birmingham prenatal clinic
- Experienced a healthy singleton pregnancy
- 5-45 weeks postpartum at enrollment
- Body mass index of 30 kg/m² or greater at enrollment
- Residing within the meal company's delivery radius
- Willing to consent

4.2 EXCLUSION CRITERIA

- Self-reported major health condition (such as renal disease, cancer, or Type 1 or Type 2 diabetes)
- Current treatment for severe psychiatric disorder (such as schizophrenia)
- Past or current diagnosis of anorexia or bulimia
- Current use of medication expected to significantly impact body weight
- Current substance abuse
- Participation in another dietary and/or weight management intervention postpartum
- Unable to understand and communicate in English
- Unwilling or unable to consume study meals

4.3 SCREEN FAILURES

Interested women who do not meet study inclusion criteria will be informed of this decision by study staff and reassured that this will not change the quality of the services and care that they receive through the University of Alabama at Birmingham.

4.4 STRATEGIES FOR RECRUITMENT AND RETENTION

Recruitment will primarily occur through UAB Center for Women's Reproductive Health (CWRH) inpatient research staff. For this, CWRH inpatient clinical research staff will perform chart reviews of women on the postpartum recovery unit (following delivery) or who are attending their 6-week postpartum checkup (6th floor of the Women and Infants Center). Participants who meet initial eligibility criteria based on the chart review will be approached by a CWRH inpatient research staff member to briefly tell the potential participant about the study, give them a study flyer, and assess initial interest. Because enrollment will not occur until participants are 5-45 weeks post-delivery, participants who are interested when approached by CWRH inpatient research staff will be asked to give their permission to be contacted when they are 5-45 weeks postpartum to remind them about the study/confirm they are still interested in participating. Participant contact information will be collected for participants who opt-in to being contacted when they are within the 5-45-week postpartum enrollment window by study staff. When potential participants recruited through the CWRH inpatient research staff are 5-45 weeks post-delivery, they will complete a secondary pre-screening by telephone to confirm eligibility. Supplemental recruitment will occur via flyers/ads distributed at UAB obstetrics/gynecological offices, UAB pediatrics clinics, UAB lactation centers, UAB Nurse Family Partnership, local day care centers and churches, local breastfeeding and/or parent support groups, and Birmingham neighborhood associations. Interested women will respond via phone call or email to the public advertisements and be screened by phone.

While participants will receive 10 free meals/week for the duration of the 8-weeks study, we will employ strategies (implemented with participants in both intervention arms) that we have found effective for retention, including: (1) providing gift cards of \$40 for completion of baseline and follow-up data collection visits, with incentives paid after each assessment; (2) ensuring frequent contacts with participants through weekly check-ins to not only obtain meal orders but also maintain engagement and foster open communication; and (3) providing reminder phone calls before scheduled study visits.

5 STUDY INTERVENTION

5.1 STUDY INTERVENTION(S) ADMINISTRATION

5.1.1 STUDY INTERVENTION DESCRIPTION

After completing baseline data collection, all participants will receive 10 fully prepared lunch/dinner-style meals per week for a total of 8 weeks. Prior studies indicate that providing 10 meals or meal replacements per week is effective for weight management.^{43,86} We are partnering with a local company, Nourish Foods, to prepare and deliver study meals. Participants will select the 10 meals that they want each week from a weekly rotating menu that includes nutrition and ingredient information to accommodate participants with food aversions or allergies. Participants place meal orders weekly with study staff who will submit orders to the meal delivery partner. During these weekly contacts, trained staff also provide brief behavioral support, including evidence-based strategies of problem-solving, action-planning, and principles of motivational interviewing to help participants identify and navigate adherence barriers.⁸⁷⁻⁹¹ Staff will document the duration and topics discussed. Each week of the intervention, participants will be automatically sent an electronic survey to report the number of study-provided meals consumed by participants (versus others in the household versus thrown out), as we understand meals may be shared in food insecure households. The study coordinator will be available when collecting weekly meal orders to help participants navigate these challenges in multi-member households. If a participant does not place their weekly order, study staff will select meals based on participant preferences and allergies collected at baseline. Meals will be delivered once per week to participants' homes, which is in compliance with the Alabama Department of Public Health guidelines.

To supplement provided meals, participants will be given a study scale and instructed to weigh themselves at least once per week and report their weekly weight measurement on an automated weekly electronic survey. The study coordinator will monitor participant weights and report any concerning weight fluctuations to the PI who is a Registered Dietitian and can make adjustments to participant meal plans as needed to support healthy weight loss postpartum. This weight measurement will also allow study staff to track participant weight gain across the intervention as the goal is to support participants in losing 0.5 to 1 kg (or 1 to 2.2 pounds) of weight per week. To support adherence to the 0.5 to 1 kg (i.e., 1 to 2.2 pound) per week weight loss, participants will be given a Weight Tracking Sheet handout to help them track their weekly weight loss. Staff will also keep a Weight Tracking Sheet for each participant. To support the healthy integration of study meals within participants' diets to promote 0.5 to 1 kg/week (i.e., 1 to 2.2 pounds/week) weight loss, participants will be given a variety of written meal plans corresponding to their individual calorie goal, as well as relevant tools (i.e., measuring cups, portion size guides) to support use of meal plans, portion control, and appropriate integration of prepared meals into participant's diets. Calories goals will be calculated using the USDA Dietary Reference Intake Calculator for Medical Professionals⁹² with gender, age, height, weight, activity

level, and lactation status as inputs, and reduced by 750 calories/day to promote weight loss of 0.5 to 1 kg per week.^{93,94} Meal plans will comply with current micronutrient and macronutrient recommendations for postpartum women.⁹⁵ Participants will also be given a Fast-Food Handout to help them select healthier meals when eating out.

5.1.2 DOSING AND ADMINISTRATION

Participants in the study receive 10 lunch/dinner-style meals per week delivered to their homes free of charge for a total of 8-weeks. Participants will select the 10 meals that they want each week from a weekly rotating menu that includes nutrition and ingredient information to accommodate participants with food aversions or allergies. Participants place meal orders weekly with study staff who will submit orders to the meal delivery partner. If a participant does not place their weekly order, study staff will select meals based on participant preferences and allergies collected at baseline to ensure they receive meals each week. Each week of the intervention, participants will be automatically sent an electronic survey to report the number of study-provided meals consumed by participants (versus others in the household versus thrown out).

5.2 STUDY INTERVENTION COMPLIANCE

Participants place meal orders weekly with study staff who will submit orders to the meal delivery partner. If a participant does not place their weekly order, study staff will select meals based on participant preferences and allergies collected at baseline to ensure they receive meals each week. Each week of the intervention, participants will be automatically sent an electronic survey to report the number of study-provided meals consumed by participants (versus others in the household versus thrown out). Study staff completing weekly check-in calls with participants will document the duration and topics discussed.

6 STUDY INTERVENTION DISCONTINUATION AND SUBJECT DISCONTINUATION/WITHDRAWAL

6.1 DISCONTINUATION OF STUDY INTERVENTION

Participants will continue to receive the study intervention for the 8-weeks study. The study intervention may be discontinued for a participant if a clinical adverse event (AE) or other medical condition or situation occurs such that continued participation in the study intervention would not be in the best interest of the subject.

6.2 SUBJECT DISCONTINUATION/WITHDRAWAL FROM THE STUDY

Subjects are free to withdraw from participation in the study at any time upon request.

An investigator may discontinue or withdraw a subject from the study for the following reasons:

- Significant study intervention non-compliance

- If any clinical adverse event (AE), laboratory abnormality, or other medical condition or situation occurs such that continued participation in the study would not be in the best interest of the subject

Subjects who sign the informed consent form, receive the study intervention, and subsequently withdraw, or are withdrawn or discontinued from the study, will not be replaced.

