1 PROTOCOL SUMMARY

1.1 SYNOPSIS

Title:	Feasibility of a meal delivery intervention for postpartum weight management
Study Description:	This is a single-group pilot study to assess the feasibility and acceptability of a meal delivery intervention among low-income postpartum women with obesity.
Objectives:	The objectives of the study are to assess the feasibility and acceptability of a meal delivery intervention among low-income postpartum mothers with obesity.
Endpoints:	The primary endpoint is participant adherence to the 8-week study intervention.
Study Population:	Participants will be 11 mothers who are 5-45 weeks postpartum, have obesity, and qualify for Medicaid or the Special Supplemental Nutrition Program for Women, Infants, and Children (i.e., have a household income at or below 185 percent of the federal poverty line).
Phase:	N/A
Description of Study Intervention:	An 8-week meal delivery intervention consisting of 10 home-delivered meals per week provided by a local meal delivery company supplemented by remote weekly behavioral support with study staff to help low-income postpartum women with obesity lose weight.
Study Duration:	8-weeks
Subject Duration:	8-weeks

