8 STATISTICAL CONSIDERATIONS

8.1 STATISTICAL HYPOTHESES

- Primary Efficacy Endpoint(s): The primary aim of this study is to assess the feasibility of the study meal delivery intervention. Hypothesis 1: We will successfully achieve >80% intervention adherence, defined as consuming at least 80% of received study meals, during the 8-week intervention.
- Secondary Efficacy Endpoint(s): The secondary aim is to characterize the acceptability of the study meal delivery intervention. Hypothesis 2a: We will collect data to characterize study participation rate and achieve <20% attrition. Hypothesis 2b: Participant reported diet satisfaction will show improvements from baseline to follow-up.

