8.3.2 ANALYSIS OF THE PRIMARY EFFICACY ENDPOINT(S)

For the primary endpoint of participant intervention adherence, the proportion of weekly study meals that participants reported a)they consumed, b) other household members consumed, and c) that were thrown away/uneaten will be calculated based on completed weekly electronic surveys.

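### Discretionary withdrawal for non-compliance can inflate the adherence endpoint, because the plan does not say how a withdrawn participant or her later weeks count

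*Combined protocol and SAP*

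**What the plan says.** The Synopsis (1.1) makes adherence the primary outcome: "The primary endpoint is participant adherence to the 8-week study intervention". Section 8.1 sets the target: "We will successfully achieve >80% intervention adherence, defined as consuming at least 80% of received study meals, during the 8-week intervention". Section 8.3.2 divides study meals into those eaten by the participant, those eaten by others in the household and those discarded, and says that these proportions "will be calculated based on completed weekly electronic surveys".

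Section 6.2 states: "An investigator may discontinue or withdraw a subject from the study for the following reasons". The first reason listed is "Significant study intervention non-compliance". No threshold for significance is given. Women who start the intervention and "subsequently withdraw, or are withdrawn or discontinued from the study, will not be replaced".

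The secondary target in 8.1 reads: "We will collect data to characterize study participation rate and achieve <20% attrition". Section 8.3.3 reports retention among enrolled participants and a CONSORT diagram.

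No section defines an analysis set for adherence, says how weeks after withdrawal count, or says whether a woman withdrawn for non-compliance is classed as non-adherent.

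**The concern.** A low value of the primary outcome is itself a permitted reason to stop observing that outcome. After withdrawal from the study a woman has no further received meals and no further completed surveys. Her remaining weeks, which would probably have shown poor adherence, then contribute nothing. This differs from ordinary dropout: the selection is on the endpoint, it is allowed by the plan, and it is at the discretion of the team whose hypothesis is being assessed.

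With 11 participants, one or two such decisions can move the summary across the 80% target. The result is meant to guide refinement of the intervention and to precede a request for funding (2.1, 8.2). An inflated figure would understate how many women the intervention did not suit.

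**Working it through.** The plan contains no power calculation or expected adherence figure to reproduce (8.2), so the check is direct arithmetic on the denominator.

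**Inputs from the documents.** 11 women (1.1, 7.1); 10 meals a week for 8 weeks, so 80 meals each and 11 × 80 = 880 in all (5.1.1); adherence target above 80% and attrition target below 20% (8.1); recruitment aim of 10 to 20 (8.2).

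**Assumed inputs.** 9 women eat 85% of their meals and 2 eat 30%, at constant rates. All surveys are returned while a woman is in the study. Meals are pooled across women.

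**1. Pooled meal level**

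If all stay: (9 × 80 × 0.85 + 2 × 80 × 0.30) / 880 = (612 + 48) / 880 = 660/880 = 75.0%.

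If the 2 are withdrawn after week t and their earlier surveys are kept: (612 + 2 × 10t × 0.30) / (720 + 2 × 10t).

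| Withdrawn after week | Eaten / received | Adherence |
|---|---|---|
| 1 | 618/740 | 83.5% |
| 3 | 630/780 | 80.8% |
| 4 | 636/800 | 79.5% |
| 6 | 648/840 | 77.1% |
| all stay | 660/880 | 75.0% |

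Attrition is 2/11 = 18.2%, so the secondary target is still met.

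Varying the rate of the 2 poor adherers, with withdrawal after week 3:
- At 20%: 644/880 = 73.2% becomes 624/780 = 80.0%, which equals the target but does not exceed it.
- At 50%: 692/880 = 78.6% becomes 642/780 = 82.3%.

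**2. Dependence on pooling**

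Section 8.3.2 does not say whether meals are pooled or proportions averaged. An average of weekly proportions also rises: weeks 1 to 3 at 75.0% and weeks 4 to 8 at 85.0% give (3 × 75.0 + 5 × 85.0) / 8 = 81.3%. An average of each woman's own proportion, keeping the withdrawn women on their early surveys, does not move at constant rates: (9 × 0.85 + 2 × 0.30) / 11 = 75.0%.

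**3. Participant level**

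The target in 8.1 can also be read as more than 80% of women each eating at least 80% of received meals. With 11 women, 9 must be adherent (9/11 = 81.8%; 8/11 = 72.7% falls short). If withdrawn women stay in as non-adherent, withdrawal changes nothing. If they are dropped:
- n = 11, 8 adherent, 2 withdrawn: 8/11 = 72.7% becomes 8/9 = 88.9% (attrition 18.2%).
- n = 10, 8 adherent, 1 withdrawn: 8/10 = 80.0% becomes 8/9 = 88.9% (attrition 10%).
- n = 20, 14 adherent, 3 withdrawn: 14/20 = 70.0% becomes 14/17 = 82.4% (attrition 15%).

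In the illustration of step 1, 9 women are adherent, so this reading gives 9/11 = 81.8% and meets the target with or without the withdrawals. The two readings can therefore disagree on the same data.

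**The case against.** The strongest reply is that the bias is conditional. Section 6.2 permits withdrawal and does not require it, and much of the protocol points towards keeping poor adherers. Staff choose meals for a woman who places no order (5.2), weekly calls help those who struggle to comply (7.1), the intervention is meant to run for the full 8 weeks (6.1), and withdrawals are not expected to be common (2.3.1). A site that never used the option would follow the plan and have no bias from this source. This stands: the documents do not show that the option was used.

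It is also fair that losses would be visible through the retention rate and CONSORT diagram (8.3.3), that the study is descriptive with no formal testing (8.3.1), and that unreturned surveys and loss to follow-up (6.3) expose the same silence in 8.3.2. Visibility does not correct the adherence figure, however, and withdrawal for non-compliance is the one route that is triggered by the endpoint itself.

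Three stronger readings are tempting, and the documents do not support them:
- A reader might infer that a withdrawn woman's poor weeks never enter the calculation. Under 8.3.2, surveys completed before withdrawal stay in; only later weeks are lost.
- A reader might infer that withdrawn women leave the participant-level count, so that everyone remaining is adherent. No section removes them. On the 8.1 definition, "defined as consuming at least 80% of received study meals", they could be classed as non-adherent on the meals they did receive. The plan leaves this open.
- A reader might measure the bias against all scheduled meals, counting those after withdrawal as uneaten: 630/880 = 71.6%, a gap of 80.8 − 71.6 = 9.2 points. At a constant 30%, the figure without withdrawal is 75.0%, so selection accounts for 80.8 − 75.0 = 5.8 points. The other 3.4 come from setting the later meals to zero.

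**Conclusion.** The point holds in conditional form. If the discretion in 6.2 is used, the pooled meal-level adherence figure rises, because the withdrawn women's below-average later weeks are removed. In the assumed case of 2 poor adherers among 11 withdrawn after week 3, the rise is 5.8 points. It turns a missed target into a met one while attrition stays below 20%. With withdrawal after week 4 or later in the same case, the figure rises but stays below 80%. The participant-level figure is affected only if withdrawn women are dropped.

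The conclusion rests on assumed eating rates that are constant over time, on full survey return before withdrawal, and on pooling over meals or weeks. It does not rest on any evidence that withdrawals for non-compliance took place. The gap merits correction because the plan has one primary endpoint and about 11 participants, and because its text allows more than one answer from the same data.

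**What to change.** Reconcile 6.2 with 8.1 and 8.3.2. No particular withdrawal rule is proposed here; the analysis should be defined whatever that rule is.

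1. **Primary summary (8.1, 8.3.2).** Report the proportion of all enrolled participants who started meals that are adherent, meaning at least 80% of meals eaten. Keep every such participant in the denominator and class anyone withdrawn for non-compliance as non-adherent.
2. **Description.** Report the meal proportions from completed surveys as now planned, stating whether meals are pooled or averaged.
3. **Sensitivity.** Give the proportion over the 80 scheduled meals per woman, counting meals after withdrawal as not consumed.
4. **Disclosure.** Report the number and timing of withdrawals for non-compliance separately from other losses. State how unreturned surveys and loss to follow-up are handled.

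This takes a few sentences and no new data. The adherence figure may come out less favourable. The 80-meal figure mixes retention with adherence and counts undelivered meals as uneaten, which is why it belongs as a sensitivity figure and not as the primary result.
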